Despite the substantial burden of chlamydia and adverse pregnancy outcomes, no previous research has been conducted to examine the effects of genital chlamydia infection on adverse pregnancy outcomes in China. There is no clinical guideline on screening for genital Chlamydia infections in pregnant women. Therefore, it is important to understand the impact of genital Chlamydia in China through randomized controlled studies that explore the relationships between Chlamydial infection and adverse pregnancy outcomes, and the feasibility and effectiveness of screening and treatment. The purpose of this study is to 1.) clarify the causal relationship between genital *C. trachomatis* infection and adverse pregnancy outcomes and 2.) determine whether screening and treatment of genital *C. trachomatis* in pregnant women can reduce adverse pregnancy outcomes. The research team will screen pregnant women in Guangzhou for genital *C. trachomatis* to understand its prevalence. We will also conduct a randomized controlled trial to explore whether clinical treatment of *C. trachomatis*-positive patients can reduce adverse pregnancy outcomes, and neonatal chlamydial conjunctivitis and pneumonia. This study will have great scientific and social significance. Firstly, it will provide

an important reference for the formulation of public health policies, clinicians' treatment of chlamydia infection in pregnant women, and prevention of chlamydial infection in newborns. Secondly, it will be a valuable resource for the prevention of adverse pregnancy outcomes and neonatal infection associated with sexually transmitted diseases in other developing countries.

II. Purpose

1. To examine whether screening and treatment of genital C. trachomatis in pregnant women can reduce adverse pregnancy outcomes
2. To explore the effectiveness of screening and treatment of genital C. trachomatis in reducing mother-to-child transmission
3. To evaluate the cost-effectiveness of screening and treating chlamydial infections in pregnant women, and provide a basis for health policy decisions on how best to screen / treat

III. Hypotheses

1. Effective screening and treatment of pregnant women with genital C. trachomatis will reduce adverse pregnancy outcomes
2. Effective screening and treatment of pregnant women with genital C. trachomatis will reduce neonatal chlamydial conjunctivitis and pneumonia
3. C. trachomatis screening and treatment of pregnant women is cost-effective.

IV. Content

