We will adopt the block randomization approach. Specific randomization steps include: 1) After we recruit participants, we will group them into blocks on a chronological basis. Each block will have 20 women who will be numbered sequentially. 2) We will then randomly divide them in each block into intervention and control groups. That is numbering the participants from 1 to 20, then generating 10 random numbers and the corresponding participants will be assigned to the intervention group. For participants in the intervention group, we will immediately test for *C. trachomatis* and *Neisseria gonorrhoeae* (See Figure 1 for the flowchart of the study design). Participants who test positive for either infection in the intervention group will be linked to physicians at the Center for treatment. For the control group, urine samples will be collected and tested immediately after childbirth or in the event of an adverse pregnancy outcome. In the event of a positive test result, the participant will be suggested to return to the Center for further treatment.

[figure not shown]

Figure 1, Flow Chart of the study.

Intervention and Treatment

This RCT will follow the principle of nonmaleficence. For pregnant women enrolled in the intervention group, after completing the test, laboratory personnel will inform the researchers of positive results. The sample number of the positive result will then be reported to the Guangzhou Women and Children Medical Center (GWCMC). The center's physicians will match the result to the correct patient and notify them of their results. We will provide a training session to the physicians at the Center about the national standard treatment plan (Azithromycin 1g, single oral administration). They will be suggested to treat patients according to the Chinese clinical and

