prevention guidelines for sexually transmitted diseases, and final decision will be made by the physician and patient together. Physicians will ask patients to return to the women's center for test of cure and re-testing in one month and three months after treatment respectively. At each of these visits, we will collect urine samples for Chlamydia testing. Patients who still test positive will continue treatment until they test negative. Additionally, pregnant women who test positive for Chlamydia will also be suggested to bring Azithromycin home to treat their spouses. We will also caution them to avoid sexual activity during the treatment period (7-10 days starting from day of treatment). We will also provide consultation services for the participants to deal with intimate partner relationship under this circumstance.

For pregnant women enrolled in the control group, we will delay the urine sample collection and the test until after delivery, or in the event of adverse pregnancy outcomes. In the event of a positive test, the patients will be informed of the positive test results the same way as the intervention group. In the event of a positive test, physicians will be suggested to provide patients and their spouses with treatment identical to the intervention group. In the event of a negative test, there will be no need for treatment. Specific treatment options will be the same to the intervention group. Physicians will ask patients to return to the Center one month after treatment for test of cure. Endpoint of the study is defined as either the occurrence of an adverse pregnancy outcome or delivery of a newborn.

After delivery, all patients who tested positive will be informed of the risk of Chlamydia infection in neonates. About 1-week post-partum (including Caesarean newborns), neonatal conjunctival scrapings and nasopharyngeal/pharyngeal swabs will be collected. In addition, infants will be examined for neonatal conjunctivitis and / or pneumonia clinical symptoms (see details in secondary outcome). In the case of a confirmed diagnosis, treatment will be carried out.

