If there is no confirmed diagnosis, family of the newborn will be advised to pay close attention for the emergence of signs of conjunctivitis and / or pneumonia, and promptly return to the hospital if the post-neonatal clinical symptoms appear. This study will follow the treatment guidelines for of the American Academy of Pediatrics Infectious Diseases and America Centers for Disease Control and Prevention for conjunctivitis and pneumonia: Erythromycin 12.5 mg/kg, oral, 4 times a day, for 14 days. For patients that do not return to the hospital for screening, the research team will call patients and verify the newborn infection status and whether treatment was provided at a different hospital.

Justifications of the control strategy

Currently in China, there are no clinical guidelines or policies that suggest routine genital chlamydia screening in pregnant women.¹⁵ The clinical standards for conducting a chlamydia test in pregnant women include relevant symptoms including urethritis, cervicitis and occurrence of adverse pregnant outcomes.¹⁵ Compared to current standard care (i.e., no routine screening and treatment), both our intervention (free screening for chlamydia at recruitment and linkage to care) and control (free screening for chlamydia at delivery of the baby and linkage to care) strategies provide better care to the target group.

Safety management plan

Criteria for withdrawal: if participants want to quit the study for any reasons; occurrence of any adverse pregnancy outcomes or recommendation by their personal physician to stop participation; Data and safety monitoring will be done by The Center and the Dermatology Hospital of Southern Medical University.

In addition, the study complies with the following statements: Any risk is the least possible for achieving the objectives of the research; Each individual providing consent is fully informed regarding the reasonably foreseeable impact of the research on the fetus or neonate; No inducements, monetary or otherwise, will be offered to terminate a pregnancy; Individuals engaged in the research will have no part in any decisions as to the timing, method, or procedures used to terminate a pregnancy; and Individuals engaged in the research will have no part in determining the viability of a neonate.

Primary Outcome

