Maternal: 1) mode of delivery: vaginal delivery or caesarean section; 2) whether twins or not; 3) occurrence of complications of childbirth, such as fetal umbilical cord around the neck, dystocia, uterine rupture and amniotic fluid embolism; 4) occurrence of stillbirth, spontaneous abortion, or premature rupture of membranes; 5) development of fetus during prenatal period (occurrence of fetal malformations and types of malformations etc.); 6) history of chronic diseases during pregnancy, including gestational diabetes, hypertension, autoimmune diseases, etc.; 7) nutritional status of pregnant woman; 8) HIV and Syphilis test and treatment information for positive cases;

9) essential clinical data: chlamydia and gonorrhea test and treatment information; 10) other clinical information: general health information (height, weight, blood pressure, blood glucose, complete blood count, urine analysis).

Neonatal: 1) Information on birth weight, neonatal death etc.; 2) occurrence of any symptoms such as conjunctivitis, pneumonia, genital infections etc.

Urine collection and laboratory testing

1) Sample collection for pregnant women with Chlamydia trachomatis / gonococcal: We will collect urine samples for testing. Before collection, we will ensure that the patient has not urinated within the last 1 hour. The patient also should not clean the sampling site in advance, such as washing etc. Patients will be instructed to collect urine in a urine cup. Urine in the urine cup cannot remain at room temperature (2-30°C) longer than 24 hours. We will use flexible pipes from the Roche cobas® PCR Urine Sample Kit, to transfer urine to the storage tube (Roche cobas® PCR Media tube). After tightening the lid, storage tubes will be turned over up and down five times. Samples will be transferred to the Dermatology Hospital of Southern Medical University for testing.

2) Neonatal samples collection: We will collect eyelid swabs (sample needs to contain eyelid epithelial cells) and pharyngeal swabs. Samples will be maintained at 2-8°C and screened within 24 hours.

3) Chlamydia trachomatis / Neisseria gonorrhoeae test: Reagent: Roche Cobas CT / NG Test kit; Instrument: Roche Cobas Z480, Roche Cobas X4800. Detection principle: CT: detecting Chlamydia MOMP gene by FAM labeling probe; NG: detecting Neisseria gonorrhoeae DR-9

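### On the likely reading of the plan, infant infection from maternal chlamydia acquired after a negative enrolment test is laboratory-ascertained only in the control arm

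*Combined protocol and SAP*

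**What the plan says.** **When mothers are tested.** Section IV, Participant recruitment and randomization, sets the timing by arm. For the intervention: "For participants in the intervention group, we will immediately test for" chlamydia and gonorrhoea. For the control: "For the control group, urine samples will be collected and tested immediately after childbirth or in the event of an adverse pregnancy outcome". Justifications of the control strategy repeats the contrast: "both our intervention (free screening for chlamydia at recruitment and linkage to care) and control (free screening for chlamydia at delivery of the baby". Enrolment is at the first hospital visit at any gestational age, so the interval between the two test times varies from woman to woman.

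**Who is retested.** Under Intervention and Treatment, women treated after a positive result come back for "test of cure and re-testing in one month and three months after treatment respectively", and "At each of these visits, we will collect urine samples for Chlamydia testing". No later test is described for an intervention woman whose enrolment test was negative.

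**Which infants are examined.** The newborn paragraph of the same section begins: "After delivery, all patients who tested positive will be informed of the risk of Chlamydia infection in neonates". It goes on to conjunctival and pharyngeal sampling and a clinical examination at about one week, then to advice to families to watch for symptoms. The sampling sentence itself does not name the infants concerned.

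**What the data are for.** Section II lists as its second purpose: "To explore the effectiveness of screening and treatment of genital C. trachomatis in reducing mother-to-child transmission". Hypothesis 2 is a reduction in neonatal chlamydial conjunctivitis and pneumonia. Secondary Outcomes lists newborn infection, conjunctivitis and pneumonia, with laboratory methods for diagnosis. Separately, Clinical Data Collection includes, for neonates without restriction by the mother's result, "occurrence of any symptoms such as conjunctivitis, pneumonia, genital infections etc".

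**The concern.** A fair comparison needs the outcome to be looked for in the same way in both arms. If infant sampling depends on the mother having tested positive, and that test falls at recruitment in one arm and at delivery in the other, the trigger itself depends on the arm.

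The group that matters is women who are negative at enrolment and infected before delivery. In the control arm the delivery test finds them and their infants are sampled. In the intervention arm nothing finds them. Analysing everyone as randomised does not repair this, because the outcome itself is missing for those infants.

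The error favours the intervention and hides a main limitation of one early screen, namely infection acquired later in pregnancy. It therefore bears on the claim about mother-to-child transmission and on any policy or cost-effectiveness conclusion drawn from it.

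**Working it through.** **Step 1. Trace each type of woman under positive-triggered sampling.**

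| Mother | Intervention arm | Control arm |
|---|---|---|
| Infected at enrolment | Positive at recruitment; infant sampled | Positive at delivery if still infected; infant sampled |
| Infected at enrolment, cured, infected again | Has tested positive; infant sampled | Not treated in pregnancy under the plan; positive at delivery; infant sampled |
| Negative at enrolment, infected before delivery | No further test described; infant not sampled | Positive at delivery; infant sampled |
| Never infected | Infant not sampled | Infant not sampled |

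The sampling rule differs between the arms only in the third row.

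**Step 2. Is there a plan figure to reproduce?** No. Sample size estimation covers adverse pregnancy outcomes only; no size or power is given for the neonatal outcomes. What follows is an illustration.

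**Step 3. Inputs.**
- From Sample size estimation: 7,725 women per arm; prevalence 6%, taken here as prevalence at enrolment.
- From the introductory background: transmission leading to conjunctivitis 15-25%, to pneumonia 5-15%.
- Assumed, because the documents give no value: a share f = 0.5% to 2% of enrolment-negative women infected by delivery, the same in both arms; no spontaneous clearance; every detected intervention woman cured and not reinfected. Losses, twins and pregnancies without a live birth are ignored.

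**Step 4. Women.**
- Infected at enrolment, per arm: 7,725 × 0.06 = 463.5.
- Negative at enrolment, per arm: 7,725 − 463.5 = 7,261.5.
- Newly infected, per arm: 7,261.5 × 0.005 = 36; 7,261.5 × 0.02 = 145.
- Infected at delivery, control: 463.5 + 36.3 = 500; 463.5 + 145.2 = 609.
- Infected at delivery, intervention: 36 to 145, none of them identified.

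**Step 5. Ratios.** With the same transmission risk in both arms, that risk cancels.
- True risk ratio: 36/500 = 0.07 to 145/609 = 0.24, a reduction of 93% to 76%.
- Apparent risk ratio: 0/500 to 0/609 = 0, a reduction of 100%.

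**Step 6. Infants not sampled in the intervention arm.**
- Conjunctivitis: 36 × 0.15 = 5 to 145 × 0.25 = 36.
- Pneumonia: 36 × 0.05 = 2 to 145 × 0.15 = 22.

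**Step 7. Sensitivity.**
- If 5% of treated women are still or again infected at delivery (463.5 × 0.05 = 23.2), the true ratio is (23.2 + 36.3)/499.8 = 0.12 at f = 0.5% and (23.2 + 145.2)/608.7 = 0.28 at f = 2%. The apparent ratio is 23.2/499.8 = 0.05 and 23.2/608.7 = 0.04.
- If f = 0, the true and apparent ratios are equal and there is no bias.
- Arm size changes the counts but not the ratios. The sample size table gives 12,874 in total at 6% prevalence, or 6,437 per arm: 6,437 × 0.94 × 0.005 = 30 to 6,437 × 0.94 × 0.02 = 121 missed women, with the same ratios.

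**The case against.** The strongest reply is that the trigger is inferred. The sentence on swabs does not name the infants, its one remark on scope concerns caesarean births, and the flow chart is not available in the text reviewed. This stands as a limit on certainty. Positive-triggered sampling is still the natural reading of a paragraph that opens with mothers who tested positive.

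Four stronger readings are tempting, and the documents do not support them.

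- *Every intervention mother is tested only once.* Treated positives are retested at one and three months. A single test describes only women negative at enrolment.
- *All infant infection from late maternal infection is looked for only among controls.* An intervention woman who was positive at enrolment and is reinfected has tested positive, so her infant falls within the sampled group.
- *Neonatal disease is undercounted only in the intervention arm.* Neonatal symptoms are listed as data for all infants, so what is lost is laboratory attribution, not every record of illness. Secondary Outcomes also puts pneumonia symptoms at 4-12 weeks, well after the one-week examination, so pneumonia can be missed in both arms.
- *The true reduction could be as low as 69%.* That comes from 145/464 = 0.31, which adds new infections to the intervention arm and leaves them out of the control arm. Counting them in both gives 145/609 = 0.24.

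It is also fair to say that this is a secondary aim worded as exploratory, and that the incidence range is assumed.

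**Conclusion.** The point holds with limits. On the likely reading of the newborn paragraph, laboratory ascertainment of infant infection differs by arm for mothers infected after a negative enrolment test, and the difference favours the intervention. The direction is clear whenever incidence after enrolment is above zero; the size is not known from the documents. Under the assumptions stated, 36-145 intervention women would go unidentified and a true reduction of 93% to 76% would be seen as 100%.

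If the sponsor meant all infants to be sampled, the arms would be treated alike, but the plan would still have to say so. The primary outcome is not affected by this point: it does not depend on the mother's chlamydia result or on infant sampling.

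**What to change.** 1. In Intervention and Treatment, state which infants are sampled and which maternal test, at what time, makes them eligible.
2. Base the Hypothesis 2 comparison on something that does not depend on arm: conjunctivitis and pneumonia in all live births, analysed as randomised, from the neonatal items already listed under Clinical Data Collection. State one data source and one time window for both arms. Give the risk difference as well as the ratio.
3. Report laboratory results from infants of test-positive mothers by arm, with the numbers of mothers positive and infants sampled, as descriptive only. Do not use them as evidence of reduced mother-to-child transmission.

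The cost is mainly protocol and analysis wording; no new tests are required. There are three drawbacks. Non-chlamydial cases pull the ratio towards 1 and add noise. Asymptomatic infant infection, part of the first-listed secondary outcome, is not compared without bias. Families told of a positive result may report symptoms more readily, and on the figures above the control arm would have 36-145 more such families. A common maternal test at delivery, or infant sampling regardless of the mother's result, would remove the difference in trigger, but either needs extra resources and the change above does not rely on it.

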Our primary outcome is the occurrence of adverse pregnancy-related outcomes between the two groups, which include: 1) stillbirth (the definition of stillbirth in this study will use International Classification of Diseases (ICD-11): death prior to complete expulsion (pregnant ≥ 28 weeks) and death during extraction [17]); 2) Spontaneous abortion (less than 1000gms or less than 28 weeks); 3) Preterm labor (birth fewer than 37 weeks gestational age; Infants born before 28 weeks are considered very early-preterm; 28-32 weeks early-preterm; 32-37 weeks late-preterm. 4) Premature rupture of membranes (prior to onset of labor); 5) Low birth weight (2,499g or less); 6) Small for gestational age (weight below the 10th percentile); and 7) perinatal death.

Secondary Outcomes

The secondary outcomes include: C. trachomatis infection of the newborn, Chlamydial conjunctivitis, and pneumonia in the newborn. Laboratory methods for the diagnosis of neonatal

chlamydial infection include: 1) Detection of *C. trachomatis* by sampling from conjunctival scraps and nasopharyngeal/ pharyngeal posterior through direct fluorescence (DFA); 2) PCR and 3) chlamydia culture.

Common Chlamydia conjunctivitis clinical symptoms and supplementary examinations include eyelid and nasal congestion, or 2) catarrhal or mucopurulent secretions, occurring within 5-14 days after birth. It is possible for exudate adhesions to form pseudomembranes. If treatment is delayed more than two weeks, conjunctival follicles may also form.

Chlamydia pneumonia infection may appear insidiously. However, symptoms will usually appear in 4-12 weeks. Common clinical manifestations include nasal mucus secretion, nasal congestion, intermittent cough, shortness of breath, rales on auscultation. There is usually no fever or change in consciousness. Laboratory examinations may show normal white count but elevated eosinophils; moderate hypoxemia on arterial blood gas; bilateral interstitial markings on chest radiography.

Clinical Data Collection

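### An adverse pregnancy outcome is listed as a reason for withdrawal although it is the primary outcome and the plan schedules maternal and infant procedures after it; the rules need reconciling so that infant data are not lost selectively.

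*Combined protocol and SAP*

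**What the plan says.** All references are to section IV of the Combined protocol and SAP unless stated.

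- **Safety management plan.** Besides a participant's own wish to leave, the withdrawal criteria include "occurrence of any adverse pregnancy outcomes or recommendation by their personal physician to stop participation". The text does not say whether withdrawal ends visits, samples, record collection or all three.
- **Primary Outcome.** "Our primary outcome is the occurrence of adverse pregnancy-related outcomes between the two groups". Of the seven components, preterm birth and the run "Premature rupture of membranes (prior to onset of labor); 5) Low birth weight (2,499g or less); 6) Small for gestational age" can all go with a live-born infant.
- **Participant recruitment and randomization.** "For the control group, urine samples will be collected and tested immediately after childbirth or in the event of an adverse pregnancy outcome". Intervention and Treatment repeats this: "we will delay the urine sample collection and the test until after delivery, or in the event of adverse pregnancy outcomes".
- **Intervention and Treatment.** "Endpoint of the study is defined as either the occurrence of an adverse pregnancy outcome or delivery of a newborn". Women who test positive are asked back for a test of cure one month after treatment. The post-delivery step covers all positive women: "About 1-week post-partum (including Caesarean newborns), neonatal conjunctival scrapings and nasopharyngeal/pharyngeal swabs will be collected". Where a woman does not come back, the team phones to establish whether the baby was infected or treated elsewhere.
- **Section II, Purpose, item 2.** "To explore the effectiveness of screening and treatment of genital C. trachomatis in reducing mother-to-child transmission". The secondary outcomes are infection, conjunctivitis and pneumonia in the newborn.

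**The concern.** The same event is the primary outcome, a reason to leave the study, and the trigger or starting point for further procedures. Site staff cannot tell whether a woman with ruptured membranes or a preterm birth is still a participant when her test of cure and her baby's swabs fall due.

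The exposed part of the trial is the infant comparison. If staff follow the withdrawal line, babies are missing because of an event that occurs after randomisation and that treatment is meant to make rarer. If treatment works, more control than intervention infants go missing, and those who remain no longer represent the randomised groups. The missing infants would be the preterm, the small and those exposed to membrane rupture. Pneumonia is the most exposed outcome, since Secondary Outcomes says its symptoms usually appear at 4 to 12 weeks. A perinatal death after membrane rupture or preterm birth could also go unrecorded as a component, although the composite would already have been met.

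**Working it through.** **Step 1. The rules side by side, for a positive woman with a preterm live birth**

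| Procedure | What section IV schedules | What the withdrawal line implies |
|---|---|---|
| Primary outcome | Met at the event | Met at the event |
| Control urine test | Triggered by the event or childbirth | Same moment; unclear |
| Test of cure | One month after treatment | For a control woman, after withdrawal |
| Infant swabs and examination | About one week after birth, no exception stated | After withdrawal |
| Phone call about the baby | If she does not return | After withdrawal |

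Preterm birth, low birth weight and small size are established at birth; only membrane rupture, among these four, can precede it. The composite is therefore recorded on either reading. The conflict lies in what follows.

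**Step 2. Inputs for an illustration**

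- 7,725 women per arm, 2% loss, odds ratio 1.8, reference event rate 10%, prevalence 6% (Sample size estimation; its table also shows 5% and 8%).
- Assumption, not in the plan: treatment removes the whole excess risk in infected women.

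The plan's total reproduces from its own 757 positive women as 757 / 0.05 / 0.98 = 15,449, which uses 5% prevalence. The 6% in the text gives 757 / 0.06 / 0.98 = 12,874. This mismatch is a separate matter, but it is a reason to show 5% beside 6%.

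**Step 3. Event rates among positive women**

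- Upward from 10%: odds 0.1/0.9 × 1.8 = 0.20, so the risk is 0.20/1.20 = 16.7% untreated, against 10% treated.
- Downward from 10%: odds 0.1/0.9 ÷ 1.8 = 0.0617, so the risk is 0.0617/1.0617 = 5.8% treated, against 10% untreated.

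**Step 4. Positive women who would leave under a literal reading**

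Positives per arm = 7,725 × 0.98 × prevalence. At 6% this is 454. Leaving = positives × event rate, for example 454.2 × 0.1667 = 76 and 454.2 × 0.10 = 45.

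| Prevalence | Positives per arm | Upward: control / intervention | Downward: control / intervention |
|---|---|---|---|
| 5% | 379 | 63 / 38 | 38 / 22 |
| 6% | 454 | 76 / 45 | 45 / 26 |
| 8% | 606 | 101 / 61 | 61 / 35 |

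These are neither upper nor lower bounds. Abortions and stillbirths leave no infant to assess, which lowers the counts. Membrane rupture is a primary component but is absent from the list behind the 10.1% cohort rate (note to the sample size table), which raises them.

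**Step 5. Is the main harm lost power?**

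Power = Φ[(|p1 − p2| − 1.96 × SE0) / SE1], where SE0 is the pooled and SE1 the unpooled standard error. The risks are low values from the background section's ranges (conjunctivitis 15–25%, pneumonia 5–15%); halving by treatment is an assumption.

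- 15% against 7.5%, 454 per arm: 0.95. With 16.7% lost in both arms: 0.91.
- 5% against 2.5%, 454 per arm: 0.51. With 16.7% lost in both arms: 0.44.

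The power cost is modest. The larger problem is that the loss depends on the outcome and can differ by arm.

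**The case against.** The strongest reply is that the withdrawal line is a stray phrase in a safety section and that the operational text overrides it. Much of this stands. Both statements on control testing make the adverse outcome the trigger for the urine sample. The post-delivery step takes in every positive woman without an exception, non-returners are phoned, and Clinical Data Collection lists neonatal death and symptoms for all. Figure 1 could not be read in the copy examined and may show what follows an event. Loss of infants is therefore one reading of conflicting rules, not an established plan. What does not stand is that the operational text settles the matter: nothing says which rule prevails, and the phone call is written for women who do not return, not for withdrawn participants, and cannot replace laboratory samples.

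A reader might infer more than the documents support:

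- **That control testing is lost.** The event itself calls for the test.
- **That the endpoint sentence removes women selectively.** It also names delivery, so if it ended follow-up it would do so for every woman before the one-week visit. It more plausibly marks when the primary outcome is reached.
- **That about 770 of 7,725 women per arm (10%) are lost against a 2% allowance.** The 2% belongs to the primary sample size, the composite is still recorded, and infant sampling appears limited to positive mothers.
- **That the size of the bias is known.** If lost infants had twice the infection risk, observed risk would be 1/(0.833 + 0.334) = 0.857 of the true value in controls and 1/(0.9 + 0.2) = 0.909 with treatment. The risk ratio would shift by 0.909/0.857 = 1.06, so 0.50 would read as 0.53. Nothing in the documents supports the doubling, and the shift is small for an objective worded as exploratory.

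**Conclusion.** The contradiction is real: the withdrawal criteria include the primary event, while the plan schedules maternal and infant procedures at or after it. Followed literally, the withdrawal line would make infant data missing according to a post-randomisation outcome, with about 76 control and 45 intervention positive women leaving at 6% prevalence, or about 45 and 26 on the downward reading. These counts rest on the plan's rates, on treatment removing the whole excess risk, and on the withdrawal line being applied.

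It is not shown that the primary outcome would be missed, that control women would go untested at the event, or that any site would apply the line this way. The importance is moderate: the analysis at risk is secondary, but infant samples not taken at one week cannot be recovered later.

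**What to change.** 1. In Safety management plan, delete the occurrence of adverse pregnancy outcomes from the withdrawal criteria. The other criteria stay.
2. There and in Intervention and Treatment, state that an adverse outcome, or delivery, is a recorded event that does not end data collection. The maternal tests and infant assessments already scheduled then continue for these women and their live-born infants.
3. State that infant outcomes are analysed by randomised arm, whatever the pregnancy outcome.

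No treatment rule changes, and swabbing need not extend beyond the infants that Intervention and Treatment already covers. Live-born infants of positive mothers remain a subset formed after randomisation, so the report should say so; the change removes an avoidable further selection.

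The cost is protocol wording, plus a few more mother-infant pairs to follow after a difficult birth.
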